10.7 PRIMARY EFFECTIVENESS ANALYSIS

10.7.1 Primary Effectiveness Hypothesis

The primary effectiveness hypothesis is that the Treatment Success rate at one year exceeds a performance goal of 80%. The hypothesis test will be evaluated using the exact binomial distribution as a one-tailed test, using significance level $\alpha=0.05$. Multivariable analyses will be used to assess predictors of success. The null and alternative hypothesis is presented below.

$$H_0: P \leq 0.80 \quad \text{vs.} \quad H_1: P > 0.80$$

Where P is the rate of Treatment Success as defined in §10.7.2.

10.7.2 Sample Size

The primary trial effectiveness variable is the Treatment Success rate at one year post-operatively. Treatment Success is a composite of clinically-relevant outcomes, including procedural technical success and freedom from: aneurysm rupture; conversion to open repair; Type I endoleak at 12 months; Type III endoleak at 12 months; clinically significant migration; aneurysm sac enlargement; or secondary endovascular procedure up to 12 months for resolution of Type I or III endoleak, device occlusion, migration, aneurysm sac expansion and/or a device defect.

The sample size is obtained by using the exact binomial distribution using PASS 2008. A sample size of 132 subjects at one year in the study population will have 80% power against a null performance goal of 80% if the proportion of Treatment Success is 88% or higher. It is estimated that the rate of Treatment Success will be greater than 88%.

It is anticipated that the drop-out rate of the trial will be 12% or less. Because the larger of the two sample sizes after adjustment for loss to withdrawal is the one for effectiveness, a minimum

of $132/0.88 = 150$ subjects will need to be recruited for this study. Thus to allow for deviations from assumptions, 150 subjects will need to be recruited for this study.

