10.2 PATIENT ACCOUNTABILITY AND MISSING DATA

The proportion of subjects with documented follow-up at each interval will be presented descriptively. The number of diagnostic, laboratory, and clinical evaluations will be tabulated by follow-up interval. Also, a listing of patients who initially consent but do not undergo a procedure due to withdrawal of consent prior to procedure will be given. However, these subjects will not be included in any analysis.

Information on missing or withdrawn subjects will be tabulated presenting the number and proportion of subjects eligible for and compliant with each follow-up examination. Subjects who withdraw from the trial will be tabulated with the reasons for the withdrawal. Additional sensitivity analyses will be performed as described below.

The evaluation of subjects with missing data presents a special concern in ITT analyses. All clinical studies analyze the results based on the completed cases (i.e., those who complete the trial). Because missing subjects do not have final data, they present a problem for ITT analyses. The statistical community recommends that multiple sensitivity analyses be conducted to determine the robustness of the result in subjects who complete the study.^{*,†‡§} The intention of these analyses is to demonstrate that the results obtained from the evaluable subjects are not biased.

As a result, sensitivity analyses using multiple imputations will be conducted to evaluate the robustness of the study result accounting for missing observations. The primary effectiveness endpoint analyses will be recalculated using an unbiased imputation of the determination of success or failure. It is expected that the number of subjects with missing effectiveness data at one year will be approximately 10% of study enrollment. The first method of imputation will be to assign values using a simple random sample from the subjects with outcomes at one year. This system is denoted the “Hot Deck by Simple Random Sampling with Replacement”.^{**} The number of subjects to impute is small and trying to

^{*}Pocock S. (1983). Clinical Trials (A Practical Approach). John Wiley and Sons, Chichester.

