10.5 POOLING

Data pooling incorporates two factors: combination of data across sites and the actual method of obtaining an estimate of the endpoint from combined data. Data will be combined from multiple study sites for the study analyses. The justification for this pooling is made on a clinical basis with three critical factors: The basis for pooling comes from: 1) The study sites must implement one common protocol; 2) The sponsor must ensure consistent application of study procedures and compliance with the protocol; and, 3) the study sites must use common data collection procedures.*

In order to determine if there is a similar response across the study sites for each response, the primary safety and effectiveness will be tested for homogeneity by extension of the Fisher's exact test (Fisher-Freeman-Halton).. If the P-value for study site is less than 0.15 for any response, differences between study site will be assumed to exist and the overall estimate of the proportion in the test subjects will be obtained by taking a weighted average of the proportions at each site with the weight being the inverse

*Meinert C. Clinical Trials: Design, Conduct, and Analysis. 1986; Oxford University Press. New York, NY

Confidential. This document and the information contained herein may not be reproduced, used or disclosed without written permission from Endologix, Inc.

of the variance of the proportion at that site.* The sum of these weighted proportions divided by the sum of the weights will be the overall estimate for the study. Both the safety and effectiveness measures will employ weighted proportions as the basis for the statistical test. The test of significance in these circumstances are fully described below in Sections 10.6 and 10.7.

If the heterogeneity P-value is less than 0.15, an analysis of the primary effectiveness endpoint by the Fleiss (1993) method will be done. The estimates obtained from this method provide a mechanism to test homogeneity and to adjust the value of the overall estimate if heterogeneity exists.

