If we assume that $P_t = 0.166$, $P_c = 0.560$, one-sided alpha = 0.025, and power = 80%, a very small number of subjects are required in the treatment group to test the above hypothesis. Should the Nellix rate be as high as 31%, then 50 subjects would provide approximately 81% power to test the primary safety endpoint at the one-sided 2.5% significance level.

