10.6.3 Analysis Plan

All subjects who receive treatment will be included in the safety analysis.

A univariate test will be done with the exact binomial distribution to determine if the frequency of MAE in the study population is statistically significantly less than 0.56. The formula for this test is provided below.

$$P(X \leq x_t | 0.56) = \sum_{k=1}^{x_t} \binom{n_t}{k} 0.56^k 0.44^{n_t-k} < 0.025$$

Where x_t is the number of study subjects experiencing an MAE and n_t is the number of subjects in the study. If the above expression holds for the observed x_t , the null hypothesis will be rejected and the alternative hypothesis will be accepted.

If there is heterogeneity among the study sites in MAE response, the analysis will be done by the method of Fleiss (1993). The test statistic will be given by the following formula.

$$z = \frac{(\bar{p}_T - 0.56)}{SE(\bar{p}_T)}$$

Where the formula for the weighted estimate of the proportion is given by the following:

$$\bar{p}_T = \frac{\sum_k W_k p_{Tk}}{\sum_k W_k}$$

And the formula for the weight in site k is given by the following:

$$W_k = \left(\frac{1}{n_k} p_k (1 - p_k) \right)^{-1}$$

And the formula for the standard error is given by the following:

$$SE(\bar{p}_T) = \left(\sum_{k=1}^{m_T} W_{Tk} \right)^{-1/2}$$

If the z has a P-value less than a one-sided alpha of 0.025, the null hypothesis will be rejected and the alternative will be accepted.

To determine those factors that may be associated with MAE, a supportive covariate analyses will be performed by logistic regression to determine if there are differences in the rates among groups when adjusted for other factors in the study population only. Covariates for these analyses will be age, gender, ASA class, cardiac/coronary artery disease (a composite variable to include arrhythmia, CHF, prior MI, CABG/PCI, heart valve repair/replacement), histories of cancer, cerebrovascular accident, coagulopathy, COPD, diabetes, hypertension, liver disease, peripheral arterial occlusive disease, renal failure, smoking, maximum aneurysm diameter, and study site. The final model will be reduced by backward elimination until no covariate terms remain in the model with a P-value less than 0.05.

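### The 80% effectiveness power stated for 132 evaluable subjects in section 10.7.2 is 76.7% under the plan's own exact test

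*Combined protocol and SAP*

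**What the plan says.** On effectiveness, section 10.7.2 names its method: "The sample size is obtained by using the exact binomial distribution using PASS 2008". It then states: "A sample size of 132 subjects at one year in the study population will have 80% power against a null performance goal of 80" per cent, provided the true success rate is 88% or higher, and adds that the rate is expected to be above 88%. On attrition it says "It is anticipated that the drop-out rate of the trial will be 12% or less", and divides 132 by 0.88 to reach 150. Section 5.1 also presents 132 as the statistically justified number.

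The test is fixed in section 10.7.1: "The hypothesis test will be evaluated using the exact binomial distribution as a one-tailed test", with alpha 0.05. Section 10.7.3 repeats it and rejects when the one-sided P-value is below 0.05. Section 10.2 gives a separate expectation for missing data: "It is expected that the number of subjects with missing effectiveness data at one year will be approximately 10% of study enrollment".

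An alternative analysis applies when sites differ. Section 10.5 says: "If the heterogeneity P-value is less than 0.15, an analysis of the primary effectiveness endpoint by the Fleiss (1993) method will be done". Section 10.7.3 then bases the test on a weighted z-statistic.

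On safety, section 10.6.2 supposes a Nellix MAE rate as high as 31% and says "then 50 subjects would provide approximately 81% power to test the primary safety endpoint at the one-sided 2.5% significance level". It does not say how that power was calculated. The planned test, in section 10.6.3, is exact: "A univariate test will be done with the exact binomial distribution to determine if the frequency of MAE" is below 0.56.

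**The concern.** Every input to the effectiveness power is stated: the method, null rate, alternative rate, alpha, sidedness and number evaluable. The figure should therefore reproduce without any assumption, and it does not.

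Effectiveness is the endpoint that sets the size of the trial, and 150 is built up from 132. If 132 does not carry 80% power, the drop-out allowance protects a number that falls short of its target. A reader weighing a missed effectiveness endpoint would also take the type II error to be 20% at the design point when it is larger.

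**Working it through.** **Inputs**

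- Null rate 0.80, alternative rate 0.88, n = 132, stated power 80%: section 10.7.2.
- One-sided exact binomial test, reject if P < 0.05: sections 10.7.1 and 10.7.3.
- Drop-out of 12% or less: section 10.7.2. About 10% missing at one year: section 10.2.

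**Trying to reproduce the 80%**

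The P-value is the upper tail P(X ≥ x) for X ~ Bin(n, 0.80), which is the sum from k = x_t printed in section 10.7.3. At n = 132:

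| Reject at | Type I error, P(X ≥ c given 0.80) | Power, P(X ≥ c given 0.88) |
|---|---|---|
| 113 or more | 0.0625 | 83.7% |
| 114 or more | 0.0383 | 76.7% |

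A cut-off of 113 exceeds 0.05, so the valid cut-off is 114. Power is 76.7%, which is 80 − 76.7 = 3.3 points below the stated figure. Type II error is 100 − 76.7 = 23.3%.

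**Other readings at n = 132**

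- One-sided 0.025, exact: reject at 115, power 68.1%.
- One-sided 0.10, exact: reject at 112, power 89.1%.
- Mid-P at 0.05: reject at 114, power 76.7%.
- The tail label in section 10.7.3, P(X > x_t), taken literally: reject at 113, power 83.7%, but type I error 0.0625.
- Normal approximation: Φ[(0.08 × √132 − 1.645 × √(0.80 × 0.20)) / √(0.88 × 0.12)] = Φ[(0.919 − 0.658) / 0.325] = 78.9%. With continuity correction it is 74.9%.

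None of these gives 80%.

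**Smallest adequate size and the attrition range**

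No n from 20 to 134 reaches 80%. The first that does is n = 135 (reject at 116 or more, alpha 0.0490, power 81.1%). Exact power does not rise steadily with n:

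| Evaluable n | Exact power at 88% |
|---|---|
| 132 to 134 | 76.7%, 75.7%, 74.6% |
| 135, 136 | 81.1%, 80.2% |
| 137 to 140 | 79.3%, 78.3%, 77.4%, 76.4% |
| 141 to 143 | 82.5%, 81.6%, 80.8% |
| 144 to 146 | 79.9%, 79.0%, 78.0% |
| 147 to 150 | 83.7%, 82.9%, 82.1%, 81.3% |

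Nine of these 19 sizes reach 80%. Two points matter most:

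- 12% loss: 150 × 0.88 = 132 evaluable, power 76.7%.
- 10% loss: 150 × 0.90 = 135 evaluable, power 81.1%.

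**Sensitivity to the true rate, n = 132.** Power reaches 80% at a true rate of 88.3% and is 86.5% at 89%.

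**Safety figure**

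Inputs are null rate 0.56, true rate 0.31, n = 50 and one-sided 0.025, from sections 10.6.1 and 10.6.2. P(X ≤ 20 given 0.56) = 0.0166 and P(X ≤ 21 given 0.56) = 0.0325, so the test rejects at 20 or fewer MAEs. Power is P(X ≤ 20 given 0.31) = 93.4%, against the stated 81%. At 132 or 150 subjects it is above 99.9%.

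**The case against.** The strongest reply is that 76.7% combines the least favourable values the plan contemplates. The 12% is a ceiling on drop-out. The only point expectation for missing one-year data is about 10%, which leaves 135 evaluable and 81.1% power. If the intention-to-treat analysis counts all 150, power is 81.3%, although section 10.7.3 defines the denominator as the number evaluated. The plan also expects a rate above 88%, and 88.3% restores 80% at 132. Counting sizes that fall below 80% is a hard cut on a saw-tooth: 144 evaluable gives 79.9%.

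All of this is correct, and it limits the weight of the point. It does not make the sentence in section 10.7.2 true, because that sentence is about 132 subjects and a rate of 88%. Lower loss does not reliably rescue it either, since power is below 80% again at 137 to 140 and at 144 to 146.

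It is also fair to say that a 3.3-point restatement changes no design decision, particularly in a revision dated April 2018, when section 8.6 shows that two-year data had already been reported in 2016. That argues for a wording correction, which is all that is proposed.

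On safety, the documents do not show which of the three linked figures is wrong. Under the exact test, 50 subjects at a 35% rate give 81.4%, and 33 subjects at 31% give 80.5%, so a misprint in either input is possible. An unstated approximate method is possible too. The 93.4% is right for the inputs as printed, but the sponsor should confirm them.

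**Conclusion.** The concern holds. For the design point given in section 10.7.2 (132 evaluable, 80% against 88%, one-sided exact test at 0.05), power is 76.7% and type II error 23.3%. No rejection rule at that size gives 80%. This rests only on inputs stated in the plan and on the summation printed in section 10.7.3.

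The consequence is modest. At a true rate of 88%, power over 132 to 150 evaluable subjects runs from 74.6% to 83.7%, so 80% is not assured across the planned attrition range and is missed at the 12% limit. Type I error, the decision rule and enrolment are unaffected. These figures describe the exact test used when sites are homogeneous and say nothing about the weighted z-test.

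The safety figure is a minor erratum in the conservative direction and does not drive the sample size.

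**What to change.** In section 10.7.2, restate the power as about 77% at 132 evaluable subjects and a true rate of 88%, rejecting at 114 or more successes (attained alpha 0.038). Add that it ranges from about 75% to 84% over 132 to 150 evaluable. Note that these values apply to the exact test and not to the weighted analysis used when the heterogeneity P-value is below 0.15.

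In section 10.6.2, confirm the 50 subjects and the 31% rate. If both stand, replace the stated 81% with approximately 93% (reject at 20 or fewer MAEs, attained alpha 0.017) and name the method.

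The cost is wording only. The stated effectiveness power becomes slightly less favourable. No subjects are added, and neither the tests nor the success criteria change.

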10.7.3 Analysis Plan

The primary effectiveness analysis will compare the Treatment Success rate as defined previously to a target rate of 80%. The null and alternative hypotheses are defined below.

$$H_0: P_t \leq 0.80$$

$$H_1: P_t > 0.80$$

Where P_t = the proportion of treated subjects who meet the Treatment Success definition. The observed proportion of subjects with Treatment Success at one year post-procedure will be tested with the exact binomial distribution under the null hypothesis given in the inequality above. The formula for this expression is presented below.

$$P(X > x_t | 0.80) = \sum_{k=x_t}^{n_t} \binom{n_t}{k} 0.80^k 0.20^{n_t-k} < 0.05$$

Where x_t is the number of successes at one year and n_t is the number evaluated. If the one-sided P-value is less than 0.05, the null hypothesis will be rejected and the study hypothesis will be demonstrated.

If the study site success proportions across study site are not homogeneous, then the method of Fleiss described above will be used in the Test arm only to obtain a weighted estimate of the proportion successful. The mean proportion is found the same way as the first equation above. The test statistic becomes a z-statistic with the following formula:

$$z = \frac{(\bar{p}_T - 0.80)}{SE(\bar{p}_T)}$$

Where the formula for the weighted estimate of the proportion is given by the following:

$$\bar{p}_T = \frac{\sum_k W_k p_{Tk}}{\sum_k W_k}$$

And the formula for the weight in site k is given by the following:

$$W_k = \left(\frac{1}{n_k} p_k (1 - p_k) \right)^{-1}$$

And the formula for the standard error is given by the following:

$$SE(\bar{p}_T) = \left(\sum_{k=1}^{m_T} W_{Tk} \right)^{-1/2}$$

If the $z < 1.645$ ($P=0.05$, one-sided), then the null hypothesis will be rejected in favor of the alternative and the primary effectiveness endpoint will be achieved.

To determine those factors that may be associated with Treatment Success, covariate analyses will be performed by logistic regression to determine if there are differences in the Treatment Success rates in the study population when adjusted for other factors. Possible covariates eligible for these analyses will be age, gender, ASA class, cardiac/coronary artery disease (a composite variable to include arrhythmia, CHF, prior MI, CABG/PCI, heart valve repair/replacement), cancer, cerebrovascular accident, COPD, diabetes, hypertension, liver disease, peripheral arterial occlusive disease, renal failure, smoking, maximum aneurysm diameter, and study site. Because there are too many possible covariates to include in a model, screening is necessary to reduce the number of eligible covariates for consideration in the final model. Screening logistic regression models to include only the covariate, will be used. If the P -value for the screening model for the covariate is less than 0.20, the covariate will be included in the competition for the final model. The final model will be obtained by manual backward elimination to have the seven or fewer covariates with P -value less than 0.05.

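### Section 10.7.3: the left side of the primary effectiveness test leaves out the observed count and does not equal the inclusive sum printed beside it (minor correction)

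*Combined protocol and SAP*

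**What the plan says.** Section 10.7.1 sets the claim: "The primary effectiveness hypothesis is that the Treatment Success rate at one year exceeds a performance goal of 80" percent. It tests this with the "exact binomial distribution as a one-tailed test, using significance level" 0.05.

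Section 10.7.3 turns this into a formula: "P(X > x_t | 0.80) = \sum_{k=x_t}^{n_t} \binom{n_t}{k} 0.80^k 0.20^{n_t-k} < 0.05". It defines the symbols as follows: "Where x_t is the number of successes at one year and n_t is the number evaluated". The decision rule is: "If the one-sided P-value is less than 0.05, the null hypothesis will be rejected and the study hypothesis will be demonstrated".

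Section 10.7.2 gives the planned size: "A sample size of 132 subjects at one year in the study population will have 80% power against a null performance goal of 80" percent, "if the proportion of Treatment Success is 88% or higher". Allowing for 12% drop-out, it recruits 132/0.88 = 150.

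No section states a pass mark as a number of successes. The parallel safety formula in section 10.6.3 has an inclusive sign (≤) on its left side.

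**The concern.** An exact one-sided P-value is the probability, at the null boundary, of a result at least as extreme as the one observed. For a success count it must include the observed count. The sum in section 10.7.3 does this and the expression to its left does not, yet the two are set equal.

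The line is the decision rule for the primary effectiveness endpoint of a single-arm study meant to support a marketing application. A programmer who works from the left side, for example as one minus the cumulative distribution at x_t, gets a pass mark one success lower. On one particular result the two sides of the equation then give opposite verdicts. A pre-specified rule should leave no room for that to be argued after the data are seen.

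**Working it through.** **Inputs.** Null boundary 0.80, one-sided level 0.05, exact binomial (10.7.1). Evaluable n = 132 and design success rate 0.88 (10.7.2). Recruited n = 150 (10.7.2). Reject if P is below 0.05 (10.7.3).

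**Formula.** For X binomial(n, p), P(X ≥ c) is the sum over k = c to n of C(n,k) p^k (1−p)^(n−k). Also P(X > c) = P(X ≥ c+1) = P(X ≥ c) − P(X = c).

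**The plan's own figure.** 132/0.88 = 150 reproduces exactly. The 80% power at 132 reproduces only approximately:

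- The normal approximation gives n = ((1.645 × √0.16 + 0.842 × √0.1056)/0.08)² ≈ 135.6, and power 78.9% at 132.
- The arcsine approximation gives power 81.1% at 132.
- The smallest n with exact power of at least 80% under the inclusive rule is 135 (pass mark 116, power 81.1%).
- Exact power at 132 is 76.7% under the inclusive rule and 83.7% under the strict one.

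The stated power therefore does not show which rule was meant. The shortfall in exact power at 132 is a separate matter.

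**Both sides of the formula at n = 132, p = 0.80.**

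| Observed x_t | Left side, P(X > x_t) | Sum, P(X ≥ x_t) | Decision by left side | Decision by sum |
|---|---|---|---|---|
| 112 | 0.0625 | 0.0967 | fail | fail |
| 113 | 0.0383 | 0.0625 | pass | fail |
| 114 | 0.0222 | 0.0383 | pass | pass |

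**Pass marks and error rates.** Size means the chance of passing when the true rate is exactly 0.80.

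| n | Rule | Pass mark | Size | Power at 0.88 |
|---|---|---|---|---|
| 132 | Sum (inclusive) | 114 (86.4%) | 0.0383 | 76.7% |
| 132 | Left side (strict) | 113 (85.6%) | 0.0625 | 83.7% |
| 150 | Sum (inclusive) | 129 (86.0%) | 0.0372 | 81.3% |
| 150 | Left side (strict) | 128 (85.3%) | 0.0590 | 87.0% |

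**Why the strict rule cannot hold 0.05.** Its pass mark c is the smallest count with P(X > c) below 0.05. Hence P(X > c−1), which equals P(X ≥ c) and is the rule's size, is at least 0.05. Equality cannot occur: at p = 4/5 every tail is an integer over 5^n, and 5^n/20 is never an integer. A check of every n from 1 to 1000 found no exception. For n = 120 to 150 the strict rule's size runs from 0.0502 to 0.0791. The inclusive rule stays below 0.05 throughout.

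**How often the choice matters.** The rules disagree only when X equals the strict pass mark. At n = 132 that is X = 113, with probability 0.0625 − 0.0383 = 0.024 at a true rate of 80% and 0.8372 − 0.7671 = 0.070 at 88%. At n = 150 it is X = 128, with probability 0.0590 − 0.0372 = 0.022 at 80% and 0.8696 − 0.8126 = 0.057 at 88%.

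**The case against.** The best reply is that the plan largely settles the matter itself. The only expression in section 10.7.3 that can be computed term by term is the sum, and the sum stands next to the 0.05 threshold. The text after it speaks of a one-sided P-value, which by convention includes the observed count. Only the inclusive rule respects the level stated in section 10.7.1. Section 10.3 also makes the SAS default the form of each exact algorithm unless otherwise specified, so a packaged procedure is more likely than hand-coding of the left-hand label. All of this stands, and it limits the point to a correction of notation.

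The sign could also be a slip of typesetting or PDF reading. That cannot be excluded. However, inclusive signs survive in the null hypothesis of the same section and in the safety formula of section 10.6.3, so a lost sign should not be assumed. Section 10.6.3 is not a clean model either, because its sum starts at k = 1 and omits zero. Printed symbols in this chapter are loose, which makes the strict sign weak evidence that a strict rule was intended.

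A reader might infer that the pass mark is truly open between 113 and 114, or that the planned test runs at an error rate above 0.05. The documents do not support either inference. The size of 0.0625 belongs to a literal reading of the left side, which the sum, the P-value sentence and the stated level all contradict.

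**Conclusion.** The printed equality is wrong and should be corrected. The governing rule is best read as the inclusive sum: at least 114 of 132, with size 0.0383. A literal coding of the left side would lower the pass mark by one success, to 113 of 132, and raise the size at a true rate of 80% to 0.0625. The one-success gap recurs at n = 150 (128 against 129).

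The consequence is confined to one count for each n. The n = 132 figures assume that the planned number is evaluated and that the unweighted exact test applies. The error is minor in scale, but it sits in a primary decision formula.

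**What to change.** In section 10.7.3, replace the left side with P(X ≥ x_t | 0.80), leave the sum from x_t to n_t as it is, and add a sentence that the inclusive tail is the P-value used for the decision.

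Rejection counts such as at least 114 of 132 or at least 129 of 150 may be added as illustrations only. The number evaluated is not known in advance. The counts also do not apply to the Fleiss z-test used when sites are heterogeneous (10.5 and 10.7.3) or to the combined P-value from multiple imputation (10.2).

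The cost is one symbol and one sentence. No data, subjects or stated error level change.

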5. STUDY POPULATION

5.1. PRIMARY INVESTIGATION

Up to 30 sites in the EU, Canada, and the United States will enroll up to 180 subjects including 30 Roll-in subjects and up to 150 patients in the Intention to Treat Pivotal Cohort for endpoint analysis. Total enrollment at a single site is restricted to 15% of the Pivotal Cohort. Following investigator training, each PI will commence patient screening and enrollment under approval per applicable national and local clinical trial requirements* and complete a minimum of one (1) successful Nellix case (Roll-in) in their training phase. This training period may be modified at the discretion of Endologix. Physicians will be directly supervised in each case by designated Endologix staff.

Pivotal Cohort: Up to 150 subjects will be enrolled at a maximum of 30 sites in the US and the EU. This includes the statistically justified sample size of 132 plus an allowance for deviations from assumptions.

Roll-In Cohort: One (1) roll-in subject may be enrolled per site, therefore a maximum of 30 enrolled in the study, to allow for Investigator(s) to receive additional training on the Nellix System. Any roll-in subjects will be screened, consented, treated and followed identically to the main study cohort. However, the roll-in cohort of this study will be evaluated separately.

* Commercially approved clinical trial requirements in the EU (CE Mark), IDE approval in the US, and ITA approval in CA

Confidential. This document and the information contained herein may not be reproduced, used or disclosed without written permission from Endologix, Inc.

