5.2. EXTENDED INVESTIGATION

Sites that participated in the Primary Investigation will be invited to participate in an Extended Investigation after enrollment closure of the primary investigation. This Extended Investigation will permit study site continued access to the Nellix System through the Primary Investigation's completion of the primary safety and effectiveness endpoint, and FDA review of the premarket approval (PMA) Submission. It is estimated that this Extended Investigation (Continued Access) phase will enroll an additional 150 patients.

Continued Access Cohort: Up to 250 patients will be enrolled into the Extended Investigation based on an enrollment rate of 0.5 patients per site per month and an estimated 20 months from the close of enrollment in the Primary Investigation. Enrollment in Extended Investigation (continued access) phase will be limited to the 27 US sites only as the Nellix System is commercially available to the three participating European sites.

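### The fallback rule for primary effectiveness is printed with the inequality reversed: it rejects H0 when z < 1.645, but H1: P > 0.80 requires z > 1.645

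*Combined protocol and SAP*

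**What the plan says.** Section 10.7.1 states the hypothesis that "the Treatment Success rate at one year exceeds a performance goal of 80" per cent, with H0: P ≤ 0.80 against H1: P > 0.80, one-tailed at 0.05. The main test in 10.7.3 is an exact binomial test that sums the upper tail.

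Section 10.5 tests the sites for homogeneity with the Fisher-Freeman-Halton test: "If the P-value for study site is less than 0.15 for any response, differences between study site will be assumed to exist". In that case the sites are combined with inverse-variance weights, and "Both the safety and effectiveness measures will employ weighted proportions as the basis for the statistical test". Section 10.7.3 then gives W_k = [p_k(1 − p_k)/n_k]⁻¹, SE = (ΣW_k)^(−1/2) and z = (weighted proportion − 0.80)/SE. Its decision rule is: "If the $z < 1.645$ ($P=0.05$, one-sided), then the null hypothesis will be rejected in favor of the alternative", upon which the endpoint counts as achieved.

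No other section restates or corrects this rule. The parallel safety fallback in 10.6.3 is worded through a one-sided P-value, so it carries no inequality on z.

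**The concern.** The statistic rises with the success rate and the alternative lies above 0.80, so rejection belongs in the upper tail. As printed, the rule is met by every z below 1.645, including large negative values from a device well under the goal. It is not met by the large positive values that a good device would produce.

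This is the stated decision rule for a primary endpoint in a branch that a pre-planned test can trigger, not a sensitivity analysis. If the branch were programmed literally, it would pass a poor device and fail a good one. If it were programmed the sensible way, the analysis would differ from the written plan, and someone could ask which rule was prespecified.

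**Working it through.** **Inputs.** H1: P > 0.80 and one-sided α = 0.05 (10.7.1). z, W_k, SE and the cut-off 1.645 (10.7.3). Switch at site P < 0.15 (10.5). n = 132 evaluable, 150 recruited, planned success rate 88% (10.7.2). Site cap (5.1): "Total enrollment at a single site is restricted to 15% of the Pivotal Cohort".

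**The plan's own figure.** The cut-off itself is right: the 95th normal percentile is 1.6449, and 1 − Φ(1.645) = 0.050. That matches the stated P = 0.05 for z > 1.645. For z < 1.645 the nominal probability at P = 0.80 is Φ(1.645) = 0.950. No alternative reading rescues the text: a reversed numerator would need z < −1.645.

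**Two observed results, all subjects as one stratum, n = 132.**
- Observed 70%: z = (0.70 − 0.80)/√(0.70 × 0.30/132) = −2.51. The printed rule says achieved.
- Observed 88%: z = (0.88 − 0.80)/√(0.88 × 0.12/132) = +2.83. The printed rule says not achieved.

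**Exact enumeration, one stratum, n = 132.** P(z < 1.645) is 0.998, 0.937 and 0.163 at true rates of 75%, 80% and 88%. This shows direction only, because one stratum cannot occur. The cap allows 0.15 × 150 = 22.5, so 22 per site, and 150/22 = 6.8 means at least 7 sites.

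**Simulation, 7 sites of 19.** Assumptions: equal sites, a common true rate, no combining of small sites, 100,000 trials per case, heterogeneity P-value by Monte Carlo.

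| True rate | Site P < 0.15 | z defined, given switch | Printed rule declares success, given switch and defined z |
|---|---|---|---|
| 75% | 14.9% | 83.4% | 88.1% |
| 80% | 14.7% | 59.2% | 49.8% |
| 88% | 13.5% | 10.9% | 1.6% |

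As a share of all trials, the branch is entered with a defined z in 0.147 × 0.592 = 8.7% at a true 80% and 0.135 × 0.109 = 1.5% at 88%. A success declared through the printed rule occurs in 0.149 × 0.834 × 0.881 = 10.9% of all trials at 75% and 0.147 × 0.592 × 0.498 = 4.3% at 80%.

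**What correcting the sign does not cure.** W_k uses the observed p_k, so sites with proportions near 0% or 100% get too much weight, and W_k is undefined at exactly 0% or 100%. Rejection by z > 1.645 at a true 80%, where z is defined:

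| Layout (assumed) | Given the switch | Regardless of the switch |
|---|---|---|
| 7 sites of 19 | 50% | 30% |
| 10 sites of 13 | 25% | 21% |
| One stratum of 132 | n/a | 6.25% |

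With 30 sites of 5, the chance that no site is at 0% or 100% is (1 − 0.8⁵ − 0.2⁵)³⁰ = 0.672³⁰, about 7 in a million at a true 80%.

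**Two editorial slips.**
- The exact P-value in 10.7.3 is labelled P(X > x_t), but the printed sum starts at k = x_t, which is the correct P(X ≥ x_t). The sum rejects from 114/132 (size 3.8%). Coding the label instead would reject from 113/132 (size 6.25%).
- The supportive safety model in 10.6.3 is reduced "until no covariate terms remain in the model with a P-value less than 0.05". That would discard the significant terms. Section 10.7.3 describes the usual direction: "manual backward elimination to have the seven or fewer covariates" that are significant at 0.05.

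**The case against.** The intent is fixed in the same sentence: a rule tagged as one-sided P = 0.05 cannot mean z < 1.645, and H1 is stated twice. A competent programmer would probably code the upper tail. This stands, and it is why the risk is a literal implementation or a prespecification dispute rather than a certain reversal.

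The text was machine-read from PDF, so a misread symbol cannot be wholly excluded, either here or in the label of the exact test. The greater-than sign does survive in H1 in the same section. The sponsor can settle this by looking at the source file.

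The seven-site layout is a minimum and not the likely one. Section 5.2 speaks of an extension "limited to the 27 US sites only as the Nellix System is commercially available to the three participating European sites", which points to about 30 sites. The Synopsis puts the 15% cap on total enrollment (27 of 180), so 6 sites could hold the 150 pivotal subjects. Section 10.4 allows small sites to be combined for site comparisons. All this affects how often z can be computed, not which way the inequality should point. With many small uncombined sites z is almost never defined, which is a fault of the branch and no defence of it.

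The percentages given the switch look larger than the shares of all trials, and both are shown above. The simulations assume homogeneous sites. Real heterogeneity would trigger the branch more often, so these shares are not upper bounds.

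Finally, the weakness of inverse-variance weighting is a separate matter from the sign, and letting another test decide would change 10.5. That is fair: the sign correction stands on its own.

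**Conclusion.** The concern holds. The printed rule contradicts its own statistic, its own alternative, its stated error level and the upper-tail exact test beside it, and nothing elsewhere corrects it. It governs the primary effectiveness conclusion whenever the site P-value is below 0.15. The direction of the error needs no assumption. The 88%, 50% and 2% rest on the assumed layout of seven equal homogeneous sites and apply only when the branch is entered and z can be computed. The main pooled exact test is unaffected. Because this is the written decision rule for a primary endpoint, it must be corrected. The two editorial slips do not bear on this conclusion.

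**What to change.** In 10.7.3, reject H0 if z > 1.645 (one-sided P = 0.05). Do not claim that this holds the type I error at 5%, and state how a site with 0% or 100% success is handled.

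Optionally, to keep a 5% test, let the pooled exact binomial test decide the endpoint whatever the heterogeneity P-value, and report the weighted estimate as supportive. This changes the deciding analysis in 10.5 and is more than an erratum.

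Editorial: relabel the exact P-value as P(X ≥ x_t | 0.80), and in 10.6.3 eliminate terms until no covariate with P greater than 0.05 remains.

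The sign and editorial corrections cost wording only, with no new data, patients or visits. Section 8.6 shows that two-year results had been reported by October 2016. The correction should therefore be a dated erratum that says whether the P < 0.15 branch was triggered and which inequality was programmed.
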